During the OLE Period, subjects will attend study visits at Weeks 52, 56, 64, and 72, and then every 12 weeks. At study visits, IMP will be administered in the clinic by sc injection as applicable. In between study visits, subjects will self-inject IMP at home. Subjects who are unable to or decide not to self-inject IMP or those without a family member/friend/caregiver who can help, will not be discontinued, but may continue to visit the site for unscheduled visits for IMP administration only.

All subjects not enrolling in the Open-Label study will have the Week 48 study assessments and will enter the SFU Period.

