**Table 7-2: Dosing scheme, OLE Period**

Week	48 (1st OLE dose)	Year 2											Year 3													
		52	56	60	64 ab	68	72 ab	76	80	84 ac	88	92	96 ab	100	104	108 ac	112	116	120 ab	124	128	132 ac	136	140		
Bimekizumab 320mg Q4W	●●	●●	●●	●●	●●	●●	●●	●●	●●	●●	●●	●●	●●	●●	●●	●●	●●	●●	●●	●●	●●	●●	●●	●●	●●	●●
Bimekizumab 320mg Q8W	●●		●●		●●		●●		●●		●●		●●		●●		●●		●●		●●		●●		●●	

OLE=Open-Label Extension; Q4W=every 4 weeks; Q8W=every 8 weeks

Notes: A bimekizumab 160mg injection is depicted by a black circle (●).

a The subject's dosing interval will change from Q4W to Q8W at Week 64 or at the next scheduled clinic visit after implementation of Protocol Amendment 5.0 if the subject has already completed the Week 64 visit.

b Subjects whose dosing interval is changed to Q8W should be dosed at this visit and will receive kits for home administration 8 weeks later.

c Subjects whose dosing interval is changed to Q8W should NOT be dosed at this visit and will receive kits for home administration 4 weeks later.

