#### 10.1.4.2 For subjects who switch from BKZ 320mg Q4W to Q8W during Open-Label Extension Period

Following Protocol Amendment 5.0, subjects receiving Q4W should switch to Q8W during the Open-Label extension period. (see Section 2.3.2.4 for further details).

Study medication duration (days)

- Attributed to BKZ 320mg Q4W:
  - Date of last BKZ 320mg Q4W dose in the OLE Period – date of first BKZ 320mg Q4W dose in the OLE Period + 28 days

Note: If date of last BKZ 320mg Q4W dose in the OLE Period + 28 days extends to a date beyond the date of first BKZ 320mg Q8W dose in the OLE Period, then this calculation reverts to:

- Date of first BKZ 320mg Q8W dose in the OLE Period – date of first BKZ 320mg Q4W dose in the OLE Period + 1.
- Attributed to BKZ 320mg Q8W use the minimum of:
  - Date of last BKZ 320mg Q8W dose in the OLE Period – date of first BKZ 320mg Q8W dose in the OLE Period + 56 days.
  - First dose date in Open-Label Extension Period 2 – date of first BKZ 320mg Q8W dose in the Open-Label Extension Period + 1.

Note: If date of last bimekizumab dose in the Open-Label Extension Period + 56 days extends to a date beyond the final visit date (including PEOT, but not including SFU), then this calculation reverts to:

- Final visit date (including PEOT, but not including SFU) – date of first BKZ 320mg Q8W dose in the OLE Period + 1.

Note: For subjects who die, if date of last bimekizumab dose in the Open-Label Extension Period + 56 days extends to a date beyond the date of death, then this calculation reverts to:

- Date of death – date of first BKZ 320mg Q8W dose in the OLE Period + 1.
- Attributed to Total BKZ
  - Sum of study medication duration in OLE period attributed to BKZ 320mg Q4W and study medication duration in OLE period attributed to BKZ 320mg Q8W-1.

Time at risk (days)

- Attributed to BKZ 320mg Q4W:
  - Date of first BKZ 320mg Q8W dose in the OLE Period – date of last BKZ 320mg Q4W dose in the OLE Period + 1 day
- Attributed to BKZ 320mg Q8W:
  - For all subjects, use the minimum of the following:
    - Date of last BKZ 320mg Q8W dose in the OLE Period – date of first BKZ 320mg Q8W dose in the OLE Period + 140 days.
    - Date of first BKZ 320mg Q8W dose in OLE2 - date of first BKZ 320mg Q8W dose in the Open-Label Extension Period + 1 day
    - Date of last clinical contact – date of first BKZ 320mg Q8W dose in the OLE Period + 1.
    - Date of death – date of first BKZ 320mg Q8W dose in the OLE Period + 1.

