### 10.3 Clinical laboratory evaluations

If not specified otherwise, laboratory values, including markedly abnormal laboratory values will be presented descriptively by treatment group for the SS. Tables presenting markedly abnormal values and those based on CTCAE grade only include selected laboratory variables.

For tables where data are summarized by visit, unscheduled and repeat visits will not be summarized, but these data will be included in listings. For tables where multiple measurements over a period of time are considered (as in shift tables), unscheduled and repeat visits will be considered as long as they were collected in the period being summarized. All summaries will be presented in SI units and will be based on observed case values. In the case where laboratory values are below the lower limit of quantification, then these will be set to the midpoint between 0 and the lower limit of quantification for the purpose of summarizing the data. The following summaries are required:

- A summary of observed results and change from Baseline values in each laboratory variable by treatment group and visit
- A summary of the number and percentage of subjects experiencing markedly abnormal values at any time while on treatment (assessment on or following the first dose of study treatment through the final dose of study treatment + 140 days) by laboratory variable and treatment group. Two separate tables will show results for the initial treatment period (for the SS) and the Initial and Maintenance Treatment Period (for the MS). An additional table for the OLE period will be provided for the OLS by treatment the subjects were receiving at the time of the assessment of the abnormal value.
- A summary of the number and percentage of subjects with a given CTCAE grade (0, 1, 2, 3, or 4) based on minimum/maximum post-baseline value by laboratory variable and treatment group. Two separate tables will show results for the initial treatment period (for the SS) and the Initial and Maintenance Treatment Period (for the MS). An additional table for the OLE period will be provided for the OLS by treatment the subjects were receiving at the time of the assessment of the value with the given CTCAE grade.

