Markedly abnormal values are defined as those with a severity of Grade 3 and above based on the common terminology criteria for adverse events (CTCAE) criteria (U.S. Department of Health and Human Services 2010). Definitions of markedly abnormal values using the Grade 3 cut points are given in the tables below for age ranges of  $\geq 17$  years (Table 10–1 for markedly abnormal liver function test values, Table 10–2 for markedly abnormal biochemistry values and Table 10–3 for markedly abnormal hematology values). Tables summarizing markedly abnormal values should include a summary (counts and percentages) of markedly abnormal labs observed at any time while on treatment (ie, treatment-emergent markedly abnormal [TEMA]). For this summary, Baseline values and values observed more than 140 days after the last administration of study medication are not considered. The laboratory results classified as Grade 3 or Grade 4 will be summarized and listed separately.

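### The OLE laboratory abnormality tables in SAP Section 10.3 show unadjusted percentages by dose at assessment, although the Q4W and Q8W columns cover unequal observation

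*SAP*

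**What the plan says.** - **Statistic.** SAP Section 10.3 asks for "A summary of the number and percentage of subjects experiencing markedly abnormal values at any time while on treatment". On treatment is defined as "assessment on or following the first dose of study treatment through the final dose of study treatment + 140 days". A companion table gives each subject's worst post-baseline CTCAE grade, and a shift table compares baseline with worst grade. All three report counts and percentages. Section 10.3 contains no rate, time at risk or per-assessment denominator.
- **OLE columns.** The markedly abnormal table is "provided for the OLS by treatment the subjects were receiving at the time of the assessment of the abnormal value". The CTCAE grade and shift tables are split "by treatment the subjects were receiving at the time of the assessment of the value with the given CTCAE grade".
- **Change of dose.** Section 10.1.4.2 says that after Protocol Amendment 5.0 "subjects receiving Q4W should switch to Q8W during the Open-Label extension period". The footnote to Table 7-2 says the interval "will change from Q4W to Q8W at Week 64 or at the next scheduled clinic visit after implementation of Protocol Amendment 5.0" if Week 64 has already passed. Section 9 plans for switches at Week 72 or 84 and at Week 96 or later. Subjects who start the OLE on Q8W have no planned switch.
- **Visits.** Section 2.3.2.4: "subjects will attend study visits at Weeks 52, 56, 64, and 72, and then every 12 weeks". The SAP does not say which of these visits include laboratory samples.
- **Grouping elsewhere.** Section 3.6 lists laboratory data among those summarized in the OLE by treatment sequence, that is, by the dose on which the subject began the OLE.
- **Adverse events.** Sections 3.6 and 10.2 also attribute events by dose, but the tables per 100 subject-years carry EAIR and EAER (Sections 10.2.1 and 10.2.2).

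**The concern.** The chance that a subject has at least one abnormal value, or a high worst grade, rises with the number of samples taken. The Q4W column holds only the OLE visits before the switch. The Q8W column holds every OLE visit of those who started on Q8W, plus the visits of switchers after the switch. A percentage that takes no account of this mixes the effect of the dosing interval with the length of observation. Equal risk can then look like a difference between the regimens, and a real difference can be masked. The adverse event tables are protected against this and the laboratory tables are not, although readers will compare the two dosing intervals on both.

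**Working it through.** The SAP states no figure here, so there is none to reproduce. The check counts visits by dose.

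**Inputs from the SAP**
- OLE clinic visits after Week 48 (Section 2.3.2.4): Weeks 52, 56, 64, 72, 84, 96, 108, 120, 132 and 144, which is 10 visits.
- A laboratory value on the day of a switch counts to the previous dose (Section 3.2).
- Allocation: 350 subjects per arm; bimekizumab re-randomized 1:2 to Q4W or Q8W at Week 16. At Week 48, PASI90 responders on Q4W or secukinumab are randomized 1:1 to Q4W or Q8W, Q8W responders stay on Q8W, and all non-responders receive Q4W (Sections 2.3.2.2 to 2.3.2.4).
- Percentages use subjects with observed data (Section 3.1). A switcher is therefore taken to enter both columns, though the SAP does not say so.

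**Assumptions**
- Laboratory samples at every OLE clinic visit, with or without one at safety follow-up (SFU).
- All 700 subjects enter, with no dropout and one common switch week.
- Week 48 PASI90 of 80 to 95% on bimekizumab (r) and 60 to 85% on secukinumab (s).
- The same risk p at every visit on both doses, independent between visits.

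**Mix at OLE start**

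Q4W starters = (350/3)(r/2 + 1 − r) + (700/3)(1 − r) + 350(s/2 + 1 − s).

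With r = 0.85 and s = 0.70: 67.1 + 35.0 + 227.5, or about 330 on Q4W and 370 on Q8W. Over the assumed ranges, Q4W starters number 274 to 362.

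**Example, switch at Week 72**
- Q4W: Weeks 52, 56, 64 and 72, so 4 visits. The switcher then has 6 visits on Q8W.
- Mean visits in the Q8W column without SFU = (370 × 10 + 330 × 6)/700 = 8.1. Ratio to Q4W = 8.1/4 = 2.0. With an SFU sample for all, 9.1/4 = 2.3.
- Percentage with at least one abnormal value = 1 − (1 − p)^k for k visits. At p = 1% with SFU: Q4W 1 − 0.99^4 = 3.9%; Q8W (370 × 10.5% + 330 × 6.8%)/700 = 8.7%.

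**Results by switch week.** The ratio range covers all assumed PASI90 mixes, with and without SFU. The percentages use r = 0.85, s = 0.70, p = 1% and SFU for all.

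| Switch week | Q4W visits | Switcher's later Q8W visits (no SFU) | Q8W/Q4W mean visits | Q4W % v Q8W % |
|---|---|---|---|---|
| 64 | 3 | 7 | 2.8 to 3.3 | 3.0 v 9.2 |
| 72 | 4 | 6 | 2.0 to 2.4 | 3.9 v 8.7 |
| 84 | 5 | 5 | 1.5 to 1.8 | 4.9 v 8.3 |
| 96 | 6 | 4 | 1.2 to 1.4 | 5.9 v 7.9 |
| 108 | 7 | 3 | 0.9 to 1.2 | 6.8 v 7.4 |
| 120 | 8 | 2 | 0.7 to 1.0 | 7.7 v 6.9 |

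**Which rate to use.** Under these assumptions a rate per assessment returns a ratio of 1. A rate per subject-year does so only if risk follows calendar time. Visits are denser early in the OLE: for a Week 72 switch, 4 visits in 24 weeks on Q4W (0.167 per week) against 8.1 in about 85 weeks on Q8W (0.096 per week). With equal risk per visit, a rate per subject-year would then favour Q8W by about 1.7.

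**Time at risk as now written.** For switchers, Section 10.1.4.2 takes Q4W time at risk as first Q8W dose minus last Q4W dose plus 1. For a Week 72 switch with the last Q4W dose at Week 68, that is 28 + 1 = 29 days. From the first OLE dose at Week 48 it is 24 × 7 + 1 = 169 days. Used unchanged, the formula would inflate the Q4W rate by about 169/29 = 5.8.

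**The case against.** A reader might infer that Q8W has about twice as many laboratory visits and so must look worse by construction. The SAP does not support that. It gives neither the laboratory schedule nor the date on which Amendment 5.0 took effect, and it plans for switches at Week 96 or later, where the excess shrinks and can reverse.

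A reader might also infer that all follow-up samples fall to Q8W. Only some do. Subjects rolling directly into OLE2 have no SFU at that point (Section 2.3.3). Those who stop while on Q4W keep their follow-up values there. With an SFU window of 20 weeks ±7 days (Section 3.1), visits on days 141 to 147 drop out, because "values observed more than 140 days after the last administration of study medication are not considered".

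Nor are these tables the only OLE laboratory comparison of the two regimens. Section 10.3 also plans by-visit summaries, which cumulative observation does not distort. Section 3.6 provides starting-dose sequences. Neutropenia and hepatic adverse events are reported per 100 subject-years.

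The arithmetic assumes independent visits. Low HDL and high LDL, both in Table 10-2, tend to persist within a subject. A persistently abnormal switcher can count in both columns, which pulls the ratio towards 1. Unscheduled samples may also count. For worst grade, the SAP does not say whether one value is taken per subject or one per dose, so the formula may not apply there.

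It can also be said that Section 3.6 sets a default and Section 10.3 is a permitted exception. The SAP does not say so for laboratory data.

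These objections limit the size and direction that can be claimed. They leave standing that the columns cover unequal observation and that nothing in Section 10.3 adjusts for it.

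**Conclusion.** The point holds in a limited form. The OLE tables of markedly abnormal values, worst CTCAE grade and CTCAE shift are unadjusted percentages over unequal observation by dose, and should not be read side by side. If samples are taken at each clinic visit and risk per visit is equal, switches at Weeks 64 to 96 inflate Q8W, with about 1.2 to 3.3 times as many visits per subject. From about Week 108 the excess is small or absent, and by Week 120 it can reverse. These figures depend on the assumed schedule, switch weeks, PASI90 mix, absence of dropout and independence between visits.

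Sections 3.6 and 10.3 need to be reconciled whatever the size of the bias. The tables are descriptive, and OLE dose depends partly on Week 48 response, so even adjusted columns would not be a randomized contrast. This is a cheap improvement to reporting and does not affect the trial's efficacy conclusions.

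**What to change.** 1. Present the OLE ever-abnormal, worst-grade and shift percentages by the starting-dose sequences of Section 3.6 and as Bimekizumab Total, and reconcile Sections 3.6 and 10.3.
2. Where results are still split by dose at assessment, add a rate per 100 subject-years to first abnormal value, or a rate per assessment. The latter is safer where visit density changes over time. State how switchers enter each denominator, and whether worst grade is taken per subject or per dose.
3. Limit any side-by-side Q4W and Q8W percentages to Weeks 48 to 64, by starting dose. A window to Week 72 would not be common to all, because Table 7-2 allows switching at Week 64.
4. Before any time at risk is used, correct the Q4W formula in Section 10.1.4.2 to run from the first Q4W dose in the OLE, not the last. Until then, only the per-assessment rate is safe.

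The cost is SAP wording and a few more table columns. No new data are needed.

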- A shift table of the number and percentage of subjects experiencing CTCAE grade 0, 1, 2, 3, or 4 values (as applicable) at Baseline to minimum/maximum post-Baseline CTCAE grade, by laboratory variable and treatment group. Two separate tables will show results for the initial treatment period (for the SS) and the Initial and Maintenance Treatment Period (for the MS). An additional table for the OLE period will be provided for the OLS by treatment the subjects were receiving at the time of the assessment of the value with the given CTCAE grade. A lipid profile table of treatment emergent markedly abnormal laboratory data will be provided for the Initial and Maintenance Treatment Period (SS) and the Open-label Extension treatment period (OLS) separately.

In addition, a shift table of number and percentage of subjects experiencing post-Baseline HDL Low risk ( $\geq 1.55$  mmol/L), Intermediate risk ( $\geq 1.04 - < 1.55$  mmol/L) and High risk ( $< 1.04$  mmol/L) compared to baseline will be provided for the Initial and Maintenance Treatment Period (SS) and the Open-Label Extension Treatment Period (OLS).

Shift laboratory summaries will use the Baseline for Open-Label Extension Period for subjects switching from secukinumab to Bimekizumab as described in Section 3.2.

A figure of neutrophil values over time for subjects with at least one markedly abnormal neutrophil value (CTCAE Grade 3 or 4) will also be presented.

A by-subject listing of all laboratory data (including urinalysis) will be provided. Separate by-subject listings for the OLE and the OLE2 treatment periods will be provided. These listings will be presented by treatment group and will include: center, subject identifier, age, sex, race, weight, visit, laboratory variable, result (with abnormal values flagged as “L” or “H” accordingly) and unit.

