**Table 10–2: Definitions of Markedly Abnormal Biochemistry Values**

Parameter Name	Conventional		Standard		Abnormal Designation
	Unit	Criteria	Unit	Criteria	
Creatinine	mg/dL	$>3.0 \times \text{ULN}$	mmol/L	$>3.0 \times \text{ULN}$	AH

Parameter Name	Conventional		Standard		Abnormal Designation
	Unit	Criteria	Unit	Criteria	
Glucose	mg/dL	<40 >250	mmol/L	<1.7 >13.9	AL AH
Calcium	mg/dL	>12.5 <7.0	mmol/L	>3.1 <1.75	AH AL
Magnesium	mg/dL	>3.0 <0.9	mmol/L	>1.23 <0.4	AH AL
Potassium	mmol/L	>6.0 <3.0	mmol/L	>6.0 <3.0	AH AL
Sodium	mmol/L	>155 <130	mmol/L	>155 <130	AH AL
Total Cholesterol	mg/dL	>400	mmol/L	>10.34	AH
HDL Cholesterol	mg/dL	<40	mmol/L	<1.04	AL
LDL Cholesterol	mg/dL	≥190	mmol/L	≥ 4.90	AH
Triglycerides	mg/dL	>500	mmol/L	> 5.7	AH

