**Table 10–4: Definitions of Markedly Abnormal Blood Pressure Values**

Parameter (unit)	Markedly Abnormal Low	Markedly Abnormal High
Systolic blood pressure (mmHg)	<90 and a decrease from Baseline of $\geq 20$	>180 and an increase from Baseline of $\geq 20$
Diastolic blood pressure (mmHg)	<50 and a decrease from Baseline of $\geq 15$	>105 and an increase from Baseline of $\geq 15$

A by-subject listing of all vital signs data will be provided. This listing will be presented by treatment group and will include center, subject identifier, age, sex, race, weight, visit, vital sign variable and result (with abnormal values flagged as “L” or “H” accordingly). This listing will also be provided separately for the OLE and the OLE2 treatment periods.

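### Treatment-emergent markedly abnormal laboratory values are counted with no condition on Baseline, so an unchanged pre-treatment abnormality is reported as emergent

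*SAP*

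**What the plan says.** Section 10.3 of the SAP asks for counts and percentages of "markedly abnormal labs observed at any time while on treatment (ie, treatment-emergent markedly abnormal [TEMA"]). The observation window is "assessment on or following the first dose of study treatment through the final dose of study treatment + 140 days". The only exclusion is that "Baseline values and values observed more than 140 days after the last administration of study medication are not considered". Nothing requires the Baseline value to be within the limit, or the on-treatment value to be worse than Baseline.

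The section states that "Markedly abnormal values are defined as those with a severity of Grade 3 and above", by CTCAE. Table 10-2 also sets limits for HDL ("HDL Cholesterol mg/dL <40 mmol/L <1.04 AL") and for LDL (4.90 mmol/L or above), and neither has a grade in Table 12-1. For these parameters: "A lipid profile table of treatment emergent markedly abnormal laboratory data will be provided", covering the Initial and Maintenance Period (SS) and the OLE (OLS).

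The section also plans CTCAE shift tables from Baseline grade to worst post-Baseline grade, and a "shift table of number and percentage of subjects experiencing post-Baseline HDL Low risk" and the other HDL risk categories. Shift summaries use the OLE Baseline for subjects who switch from secukinumab.

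**The concern.** A count labelled treatment-emergent should describe something that appeared or worsened after treatment began. Under this rule, a subject beyond the limit before the first dose who stays there unchanged is a TEMA case.

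Elsewhere the SAP uses the idea differently:

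- Section 9.3.2 counts as treatment-emergent antibody positive only Baseline-negative subjects who turn positive and Baseline-positive subjects with a boosted titer. Unchanged positives form their own category and are left out of the total.
- Table 10-4 defines markedly abnormal low systolic pressure as "<90 and a decrease from Baseline of" at least 20 mmHg, so the limit alone is not enough.

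The laboratory rule has no such element, and no reason is given. At stake is how the TEMA percentages are read. The exposed parameters are those whose limit may be common before treatment. HDL is the clearest example, because its limit coincides with the SAP's own 'High risk' category.

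**Working it through.** The SAP states no TEMA rate and no Baseline lipid distribution, so there is no figure of its own to reproduce. Everything below except the arm size of 350 (Section 2.4) and the cut-offs is an assumption, shown as a range.

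**1. Formula.** Let p be the proportion beyond the limit at Baseline. Let r be the chance that such a subject has at least one on-treatment value beyond it, and i the same chance for a subject within the limit at Baseline.

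- Flagged = p·r + (1 − p)·i
- Share of flagged subjects already abnormal at Baseline = p·r / flagged

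The pre-existing part of the percentage is p·r, so it can never exceed p. For limits that few subjects meet at Baseline, the effect on the percentage is therefore small.

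**2. HDL below 1.04 mmol/L.** Assumed p 5–40%, r 80–95%, i 2–20%.

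- Lowest share (p = 5%, r = 80%, i = 20%): 0.04 / (0.04 + 0.19) = 17%
- Highest share (p = 40%, r = 95%, i = 2%): 0.38 / (0.38 + 0.012) = 97%

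The second column of results comes from a simulation with no drug effect: lognormal values, between-subject CV 25%, within-subject CV 5–12%, 3 to 10 post-Baseline visits.

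| Baseline prevalence | Pre-existing share, formula | Pre-existing share, simulation |
|---|---|---|
| 5% | 17–71% | 30–67% |
| 10% | 31–84% | 36–71% |
| 20% | 50–92% | 45–76% |
| 30% | 63–95% | 52–80% |
| 40% | 73–97% | 58–83% |

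At 20% prevalence the simulation flags 25–43% of all subjects as treatment-emergent although the drug does nothing.

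**3. Double-blind contrast.** Suppose new abnormality truly occurs in 10% versus 5% (risk ratio 2.0), with r = 90% in both arms.

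- p = 10%: (0.09 + 0.90 × 0.10) / (0.09 + 0.90 × 0.05) = 0.180 / 0.135 = 1.33
- p = 30%: (0.27 + 0.70 × 0.10) / (0.27 + 0.70 × 0.05) = 0.340 / 0.305 = 1.11

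The true difference of 5 percentage points shows as 4.5 and 3.5.

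**4. OLE.** There is no comparator, so p·r is simply added to the reported percentage. Section 3.2 defines an OLE Baseline for secukinumab switchers in selected laboratory summaries, but Section 10.3 assigns it only to the shift summaries. A switcher with low HDL throughout secukinumab treatment who stays low is counted as emergent on bimekizumab.

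**5. LDL.** Assume mean 2.9–3.3 mmol/L, between-subject SD 0.85, within-subject SD 0.3, 10 post-Baseline values and no drug effect. Then 4–9% of subjects are flagged, and 31–37% of those were already beyond the limit. That is about 1% (0.04 × 0.31) to 3% (0.09 × 0.37) of all subjects.

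**6. With a Baseline condition.** Take p = 20%, r = 95%, i = 5% in an arm of 350.

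- As written: 70 × 0.95 + 280 × 0.05 = 66.5 + 14 = 80.5, or 23% of 350
- With the condition: 14 of 280, or 5%

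**The case against.** The best defence is that the SAP already shows Baseline status for most parameters. The HDL shift table uses the same 1.04 mmol/L limit, and the same sets and periods, as the lipid TEMA table. Total cholesterol and triglycerides are graded in Table 12-1, so the CTCAE shift tables cover them. Observed values and change from Baseline are summarised by visit for each laboratory variable, LDL included. The laboratory tables are descriptive, with no test attached. Randomisation balances Baseline abnormality on average, so neither arm is favoured. Table 10-4 is not an exact precedent either: a subject already beyond the blood-pressure limit who changes by the stated amount still counts.

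Most of this stands, and it limits the harm. It does not repair the TEMA percentage, which still carries a label the rule does not deliver. LDL has a TEMA limit but neither a grade nor a shift table. The same is true of low glucose, which has a limit in Table 10-2 but only a high-glucose row in Table 12-1. Table 10-4 remains relevant as evidence that the SAP elsewhere requires change, not as a template.

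A reader might infer that the lipid tables would mostly report pre-existing low HDL. The documents do not support that. They give no HDL distribution, and the share is at least half throughout the assumed ranges only from about 30% Baseline prevalence.

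**Conclusion.** The definitional fault is on the face of Section 10.3 and needs no assumption: an unchanged pre-treatment abnormality is counted as treatment-emergent. Its size does need assumptions. For HDL, between about 17% and 97% of TEMA cases could be pre-existing; for LDL the illustration gives about 1–3% of all subjects; for rare Grade 3 limits the effect is likely small.

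In the double-blind period the consequence is dilution. A reader might infer bias towards one arm or a spurious difference between arms, but with randomised groups nothing in the SAP points to either. In the OLE the emergent percentage is inflated, and for secukinumab switchers the wrong reference point adds to this. The shift tables are a partial safeguard, which makes this a change worth making rather than a critical defect.

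That HDL and LDL lack a CTCAE grade although the section defines markedly abnormal as Grade 3 and above is a separate definitional matter. It bears on this point only because such limits may be commonly met at Baseline.

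**What to change.** In Section 10.3:

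- Define a TEMA subject as one who does not meet the Table 10-1, 10-2 or 10-3 criterion at Baseline and meets it on treatment.
- For every parameter, use as denominator the subjects who do not meet the criterion at Baseline. Leave worsening from Grade 3 to Grade 4 to the CTCAE shift tables, so that numerator and denominator describe the same subjects.
- For secukinumab switchers in the OLE, use the OLE Baseline of Section 3.2.
- Keep the present count as a separate row labelled as markedly abnormal at any time on treatment.
- Add an LDL shift table from Baseline to worst post-Baseline value.

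The cost is a wording change, one Baseline condition in the programming and one more table; no new data are needed. Denominators will vary slightly by parameter. For ungraded HDL and LDL, further worsening in a subject already beyond the limit will not count as TEMA, although that subject stays visible in the any-time row and contributes to the change-from-Baseline summaries.
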